## 5. Introduction

### 5.1. Background

An estimated 8.5 million people in the United States will have heart failure (HF) by 2030 [1], and approximately 50% of these HF patients will have a preserved ejection fraction (HFpEF) [2]. In contrast to HF with reduced EF (HFrEF), no effective drug or device therapies have been identified that improve the prognosis of the disease.

A large proportion of HFpEF patients have hypertension and have a concentric hypertrophic (CH) etiology described as an increased heart mass with increased relative wall thickness [3]. Cardiomyocytes in HFpEF are thicker than HFrEF, and collagen content is increased compared to controls [4]. Patients with concentric hypertrophy or evidence of increased wall thickness are characterized by an increase in end diastolic pressures and isovolumic relaxation time [5] compared to normal controls. HFpEF patients have relatively normal volumes and EF, but they have a reduced ability to adequately fill a stiffened left ventricle (LV). The impact of this diastolic dysfunction is more notable during exercise; HFpEF left ventricles are reliant on high left atrial pressures to fill the LV [4]. A search for a therapy that improves the compliance of the ventricle and improves early diastolic filling in these patients has not been successful.

We are proposing a pacing therapy that titrates a bolus of atrial pacing at 100 bpm delivered during sleeping hours with the hypothesis that raising heart rates can promote a beneficial LV dilation, which will reduce chamber stiffness and improve diastolic filling in HFpEF patients that have thickened ventricular walls and normal to small LV volumes. One challenge is finding a therapeutic heart rate dose that does not cause undesirable symptoms in ambulatory HF patients and a dose that achieves a desirable level of dilation to improve filling. Studies in animal models show that the dilatory effects of rapid pacing diminishes once the elevated pacing rates are discontinued [6-8] ; the study of dose response to elevated atrial pacing rate also includes monitoring the reaction of the heart to withdrawal of the pacing therapy.

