### **6.2. Endpoints**

As part of the exploratory/ancillary safety, tolerability and efficacy effects described in Section 14.1. Endpoint Definitions, it will be of interest to characterize changes in collected measurements from Baseline to 4 weeks, compare changes in collected measurements at 4 weeks to 8 weeks in the subjects randomized to the elevated night pacing ON arm to subjects randomized to the elevated night pacing OFF arm and compare changes in collected measurements at 12 weeks to Baseline, 4 and 8 weeks to see whether any therapeutic improvements are sustained after the therapy is discontinued.

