### 7.2. Rationale

It is expected that up to 50 subjects may be enrolled to ensure approximately 30 subjects will have elevated night pacing programmed ON for the first 4 weeks in order to evaluate whether the therapy is symptomatic. Limitations to the programming of the Sleep Function requires subjects to have a lower

rate of 100bpm programmed between the time they leave the Baseline visit and 5am the next morning when "Bed Time" will set the Sleep Rate at the pre-study lower rate of 60-70bpm. At the 4 week visit, there will be a safety assessment. Measurements of NT-proBNP will be used to assess whether dilation of the heart is signalling worsening heart failure. A Troponin assay will be used to ensure the elevated night pacing therapy isn't leading to ischemia. Subjects will be randomized at 4 weeks to elevated night pacing ON or OFF in order to gather data on the dose-response of the elevated night pacing therapy. Some patients may have sensation of an elevated heart rate from this programming, making blinded randomization difficult to achieve. All subjects will be followed for at least 4 weeks following termination of the elevated night pacing therapy in order to evaluate whether changes in quality of life, 6 minute walk tests and echo measurements persist after the therapy is discontinued. Previous work in animal studies have shown that cessation of elevated pacing rates can reverse the dilation of the LV chamber; this study will monitor the time course of that reversal by serial echo measurements, 6 minute walk tests and activity counts, and quality of life assessments.

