## **Device-measured activity levels – 8 weeks**

### Hypothesis

There is an improvement in daytime activity levels over an additional 4 week period of elevated night pacing after an initial 4 week period of elevated night pacing compared to that period of 4 weeks with the elevated night pacing programmed OFF after the initial 4 weeks period of elevated night pacing.

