### Analysis Methods

Activity levels over time will be characterized over time from the 4 week visit to the 8 week visit and compared between the subjects with the elevated pacing programmed ON versus OFF. Analysis will be similar to the 4 week activity level endpoint. The date of the 8 week visit and the 3 days prior to and subsequent to it will comprise the 8 week window.

Those periods will be retrieved from the Cardiac Compass activity level data using SAS code similar to the following

```
DATA Activity_Week8;
  SET Activity_Consent;

  /*      Straddle the week 4 date - the 4 week date and the 3 days
  before and after the 4 week date */
  IF (w4date-3) LE entryday-consdt LE (w4date+3) THEN DO;
    period=1;
    OUTPUT;
  END;

  /*      Straddle the week 8 date - the 8 week date and the 3 days
  before and after the 8 week date */
  IF (w8date-3) LE entryday-consdt LE (w8date+3) THEN DO;
    period=2;
    OUTPUT;
  END;

RUN;
```

The analysis will be performed using linear mixed effects modeling, using SAS code similar to

```
PROC MIXED DATA=Activity_Week8;
  CLASS pt period trt;
  MODEL activityperday = period trt period*trt;
  RANDOM pt;
  LSMEANS period trt period*trt / PDIFF=all ALPHA=0.05;
RUN;
```

A significant p-value for the interaction between period and treatment would suggest that there is incremental value in continuing high rate pacing from week 4 to week 8.

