##### Analysis Methods

These analyses will be exploratory in nature, involving characterizing changes from baseline and end of therapy to the last follow-up visit. Generally speaking, all tests described above may be analyzed at week 12 compared to baseline, week 4 or week 8. Specific tests of interest will include

- For any measurement found significant at week 4
  - A test for subjects with high rate pacing set to OFF at week 4 will be done to compare the measurement at week 8 with both baseline and week 4

- A test for subjects for subjects with high rate pacing set to ON at week 4 will be done to compare the measurement at week 12 with baseline, week 4 and week 8
- For any measurement found significant by treatment at week 8
  - A test for subjects with rate pacing set to ON at week 4 will be done to compare the measurement at week 12 with baseline, week 4 and week 8

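### The week-8 activity rule in SAP 7.9.5 reads any significant period-by-treatment interaction as added value of weeks 4 to 8, without requiring its sign or separating a gain in ON from a loss in OFF

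*SAP*

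**What the plan says.** Protocol 7.2 gives the purpose of the second randomised period: "Subjects will be randomized at 4 weeks to elevated night pacing ON or OFF in order to gather data on the dose-response". Nominally, the ON arm is paced for 8 weeks and the OFF arm for 4.

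SAP 7.9.5 (Device-measured activity levels – 8 weeks) has a directional hypothesis, "There is an improvement in daytime activity levels over an additional 4 week period of elevated night pacing", judged against the same 4 weeks with pacing OFF. The model is "MODEL activityperday = period trt period*trt", with a random subject effect. The section closes by saying that a significant interaction p-value "would suggest that there is incremental value in continuing high rate pacing from week 4 to week 8". It sets no condition on the sign or on what the ON arm itself did.

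Protocol 5.1 reports from animal work that "the dilatory effects of rapid pacing diminishes once the elevated pacing rates are discontinued", and Protocol 7.2 repeats that stopping can reverse the dilation and says the study will follow that reversal.

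For the period after therapy, Protocol 6.2 intends to "compare changes in collected measurements at 12 weeks to Baseline, 4 and 8 weeks". SAP 7.9.8 describes this generally as change from baseline and from end of therapy to the last visit, then lists specific tests. The only listed test for the OFF arm reads, in part: "high rate pacing set to OFF at week 4 will be done to compare the measurement at week 8 with both baseline and week 4". The other listed tests take the ON arm to week 12.

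**The concern.** At week 8 the arms differ in two ways at once: how long they have been paced, and how long since pacing stopped. Randomisation does not separate these, because both follow from the assignment. If the benefit is complete by week 4 and then fades in OFF, the interaction favours ON although weeks 4 to 8 added nothing. The activity rule would call that incremental value. Because the rule rests on a p-value alone, worsening in ON, or improvement in OFF once pacing stops, also satisfies its wording.

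What is at stake is interpretation. A result showing that the effect wears off could be reported as evidence that 8 weeks of pacing does more than 4.

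**Working it through.** **The plan's own figures.** There is none to reproduce for this contrast. SAP section 6 rests the sample of up to 30 on the confidence-interval width for the 4-week tolerability proportion. It gives no power, effect size or SD for activity.

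**Inputs**
- 2:1 allocation (Protocol 7, SAP 5.1). With all 30 subjects reaching randomisation (assumption), this is 20 ON and 10 OFF.
- Time off therapy in OFF at the week-8 visit: nominally 4 weeks. From the windows in Protocol Table 5 it runs from 49 − 35 = 14 days to 63 − 21 = 42 days.
- Significance level: the SAP code sets 0.05 for the LSMEANS output and writes none for the interaction, so two-sided 5% is assumed. The interaction F test has no direction.
- Effect sizes d, in SDs of the subject-level week 4-to-8 change: assumed.

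**What the interaction measures**

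Interaction = (ON week 8 − ON week 4) − (OFF week 8 − OFF week 4). In arbitrary units:

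| Pattern | ON change | OFF change | Interaction |
|---|---|---|---|
| Further gain in ON, OFF stable | +1 | 0 | +1 |
| ON flat, OFF fades fully | 0 | −1 | +1 |
| ON loses half, OFF loses all | −0.5 | −1 | +0.5 |
| ON worsens, OFF stable | −1 | 0 | −1 |
| Harm by week 4, relieved in OFF | 0 | +1 | −1 |

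The first two rows cannot be told apart by the interaction. The third favours ON while ON declines. The last two count against pacing, yet a significant result in either satisfies the rule as worded.

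**How often the rule would be met**

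Two-sample t test on subject-level changes, df = 20 + 10 − 2 = 28, noncentrality = d / √(1/20 + 1/10) = d / 0.387.

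| Net difference d | Noncentrality | Significant, two-sided 5% |
|---|---|---|
| 0.5 | 1.29 | 24% |
| 0.8 | 2.07 | 51% |
| 1.0 | 2.58 | 70% |
| 1.2 | 3.10 | 85% |

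The figures are the same for +d and −d. A 1 SD loss in OFF with ON flat, and a 1 SD disadvantage in ON, therefore each meet the rule about 70% of the time.

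A sign requirement alone does not settle the matter. In a one-sided 5% test such as the one stated for the walk test, with no change in ON, the chance of declaring ON better is 35%, 60% or 81% if OFF loses 0.5, 0.75 or 1.0 SD.

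**With the sign and the ON arm's own change required**

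Suppose added benefit is claimed only if the contrast favours ON and ON's own week 4-to-8 gain is significant at two-sided 5%. The case of ON flat and OFF down 1 SD is then called added benefit at most 2.5% of the time. A 1 SD disadvantage in ON is called added benefit less than 0.1% of the time.

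**A limit specific to activity**

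The activity windows are the visit day and 3 days either side, so 3 of 7 days follow reprogramming: in OFF at week 4 and in ON at week 8. If the benefit disappears the day after switch-off, only 0.14 of it appears in the interaction. With linear fading over 7, 14 or 28 days the share is 0.76, 0.88 or 0.91. The misreading is thus most likely when the effect fades over days to weeks.

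**The case against.** Much of the case on the other side stands.

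- The contrast answers the question posed. The hypothesis in SAP 7.9.5 sets 4 more weeks ON against 4 weeks OFF. If stopping loses a benefit, continuing has value relative to stopping. Protocol 14 also gives the ON-OFF comparison another legitimate use: showing a treatment effect under blinding, which the open single-arm first 4 weeks cannot do. Protocol 5.1 counts monitoring of withdrawal as part of studying dose response. A reader might infer that the randomised comparison is invalid; the documents do not support that.
- A reader might infer that every week-8 test has this feature. It does not: the first EQ-5D-5L test compares week 8 with baseline and has no arm term.
- A reader might infer that harm would be reported as benefit. The activity hypothesis is directional, the LSMEANS output shows signed differences, and the walk-test, MNLWHF and EQ-5D-5L hypotheses are one-sided. The missing sign is a gap in one sentence for one endpoint; 70% is the chance of significance, not of a misreport.
- A reader might infer that the OFF arm's week-12 data go unused. SAP 7.9.8 covers change from baseline and end of therapy to the last visit in general terms for subjects with follow-up after switch-off, and SAP 4.2 carries effects significant at week 4 to weeks 8 and 12. What is absent is the OFF arm at week 12 among the listed tests.
- Comparing ON at week 12 with OFF at week 8 equalises nominal time off therapy, but introduces a 4-week difference in follow-up time. It does not isolate duration.
- No passage says the week-8 contrast will set the duration of a later study. Protocol 14 and SAP section 6 name the 4-week safety and tolerability result as the one that helps decide whether to proceed.

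None of this supplies the missing sign or separates a gain in ON from a loss in OFF. The LSMEANS and t-test output would show each arm's change, but the SAP does not tie its conclusion to it.

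**Conclusion.** The point holds for the interpretation rule, not for the randomised design. The closing sentence of SAP 7.9.5 on week-8 activity claims more than a significant interaction can show. The week 4-to-8 between-arm contrasts support a conclusion about continuing versus stopping. By themselves they do not establish added benefit from weeks 4 to 8 or a duration effect.

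The 70% figures rest on an assumed 1 SD difference, 20 and 10 subjects with no attrition before randomisation, and an analysis of subject-level changes. The planned random-intercept model on daily values could give other rates. The expectation of reversal comes from animal work on left ventricular dilation; the documents give no estimate of fading for activity, walk distance or quality of life. These are exploratory, unpowered analyses, so the consequence is a wrong reading of a result, not a failed primary test.

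**What to change.** 1. In SAP 7.9.5, replace the closing sentence on week-8 activity with a signed period-by-treatment estimate and confidence interval. State that only a contrast favouring ON supports continuing versus stopping.
2. Beside every ON-OFF contrast, report each arm's own week 4-to-8 change with its confidence interval. Describe a positive contrast with no gain in ON as *effect lost on withdrawal*, not as added benefit.
3. In SAP 7.9.8, add the OFF arm's week 12 versus weeks 4 and 8 to the listed tests.
4. Optionally, add a supportive exploratory table of ON change from baseline to week 12 against OFF change from baseline to week 8. State that nominal time off therapy is equal, but that the comparison is confounded with follow-up time and does not isolate duration.

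The cost is SAP wording and a few tables from visits already scheduled. Treatment, visits and sample size are unchanged.

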#### Determination of Subjects for Analysis

All subjects that completed 4 weeks of elevated night pacing. Daytime activity levels up to time of exit will be used for subjects that do not complete the full 4 weeks of participation in the study from week 4 to week 8.

#### 7.9.6. Ancillary Efficacy Endpoint – Echo Measurements

##### **Echo measurements – 4 weeks**

###### Hypothesis

All echo measurements will be assessed to see if there are changes from baseline after a 4 week period of elevated night pacing.

###### Analysis Methods

A paired comparison of the value at the end of the period compared to the value at the start of the period will be calculated. A two-sided paired t-test will be performed testing the hypothesis

$$H_0: \mu = 0$$

$$H_a: \mu \neq 0$$

Where  $\mu$  = difference in measurement from baseline to week 4 visit

SAS code similar to the following will be used to evaluate any echo measurement assessed as a continuous variable:

```
PROC TTEST;
```

```
PAIRED echotestn_0* echotestn_4;  
RUN;
```

If any of the echo measurements of interest are collected as categorical variables with binary outcomes, the data will be reshaped to a vertical data file with columns for subject id, echo test value (0 or 1) and time, which will be 0 for the baseline echo and 4 for the 4 week echo, unless the subject exited the study early, in which time will be calculated as the time elapsed from baseline to exit. Then, a general linear mixed model will test whether there was an improvement in the echo test over time, using SAS code similar to:

```
PROC GLIMMIX;  
  CLASS pt time;  
  MODEL echotest = time / dist=binary link=logit;  
  RANDOM intercept / subject=pt;  
RUN;
```

### Determination of Subjects for Analysis

All subjects that completed 4 weeks of elevated night pacing. Subjects that were unable to tolerate or withdrew from the treatment during the first 4 weeks because of safety or other issues will not be included in this efficacy analysis.

### **Echo measurements – 8 weeks**

#### Hypothesis

All echo measurements will be assessed to determine whether there is a difference in the change of the measurement following an additional 4 week period of elevated night pacing after an initial 4 week period of elevated night pacing compared to that period of 4 weeks with the elevated night pacing programmed OFF after the initial 4 weeks period of elevated night pacing.

#### Analysis Methods

A paired comparison of the measurement at the 8 week visit compared to the score at the 4 week visit period compared to the value at the start of the period will be calculated. A two-sided paired t-test will be performed testing the hypothesis

$$H_0: \mu_{ON} = \mu_{OFF}$$

$$H_a: \mu_{ON} \neq \mu_{OFF}$$

Where  $\mu_{ON}$  = difference in echo measurement from week 4 to week 8 in subjects randomized to the ON arm and  $\mu_{OFF}$  = difference in echo measurement from week 4 to week 8 in subjects randomized to the OFF arm

SAS code similar to the following will be used to evaluate the effect of the study therapy between week 4 and week 8 on echo measurement assessed as continuous variables:

```
PROC TTEST;  
  CLASS trt;  
  VAR echotestdiff;  
RUN;
```

If any of the echo measurements of interest are collected as categorical variables with binary outcomes, the analysis will be done similar to the comparison between the 4 and 8 week measurements. An extra column, indicating the treatment arm will need to be included. The analysis will be performed using SAS code similar to

```
PROC GLIMMIX DATA=EchoTime2 METHOD=RMPL;  
  CLASS pt time trt;  
  MODEL echotest = time trt time*trt / dist=binomial link=logit;  
  RANDOM intercept / subject=pt;  
RUN;
```

#### Determination of Subjects for Analysis

All subjects that completed 4 weeks of elevated night pacing. Echo measurement at time of exit will be used for subjects that do not complete the full 4 weeks of participation in the study from week 4 to week 8.

#### 7.9.7. Ancillary Efficacy Endpoint – Collagen Degradation Biomarker Measurements

##### **Biomarker measurements – 4 weeks**

###### Hypothesis

If the results of the safety, tolerability and efficacy of elevated night pacing appear to be promising, additional work may be done to assess collagen degradation biomarker measurements to see if there are changes from baseline after a 4 week period of elevated night pacing.

###### Analysis Methods

A paired comparison of the value at the end of the period compared to the value at the start of the period will be calculated. A two-sided paired t-test will be performed testing the hypothesis

$$H_0: \mu = 0$$

$$H_a: \mu \neq 0$$

Where  $\mu$  = difference in measurement from baseline to week 4 visit

SAS code similar to the following will be used to evaluate the change in each relevant biomarker measurement:

```
PROC TTEST;
  PAIRED biomarkern_0* biomarkern_4;
RUN;
```

### Determination of Subjects for Analysis

All subjects that completed 4 weeks of elevated night pacing. Subjects that were unable to tolerate or withdrew from the treatment during the first 4 weeks because of safety or other issues will not be included in this efficacy analysis.

### **Biomarker measurements – 8 weeks**

#### Hypothesis

If the results of the safety, tolerability and efficacy of elevated night pacing appear to be promising, additional work may be done to determine whether there is a difference in the change in the collagen degradation biomarker measurements following an additional 4 week period of elevated night pacing after an initial 4 week period of elevated night pacing compared to that period of 4 weeks with the elevated night pacing programmed OFF after the initial 4 weeks period of elevated night pacing.

#### Analysis Methods

A paired comparison of the measurement at the 8 week visit compared to the score at the 4 week visit period compared to the value at the start of the period will be calculated. A two-sided paired t-test will be performed testing the hypothesis

$$H_0: \mu_{ON} = \mu_{OFF}$$

$$H_a: \mu_{ON} \neq \mu_{OFF}$$

Where  $\mu_{ON}$  = difference in collagen degradation biomarker measurement from week 4 to week 8 in subjects randomized to the ON arm and  $\mu_{OFF}$  = difference in collagen degradation biomarker measurement from week 4 to week 8 in subjects randomized to the OFF arm

SAS code similar to the following will be used to evaluate the effect of the study therapy between week 4 and week 8 on each biomarker measurement:

```
PROC TTEST;
  CLASS trt;
  VAR biomarkerdiff;
RUN;
```

#### Determination of Subjects for Analysis

All subjects that completed 4 weeks of elevated night pacing. Biomarker measurement at time of exit will be used for subjects that do not complete the full 4 weeks of participation in the study from week 4 to week 8.

#### 7.9.8. Ancillary Efficacy Endpoint – Sustained effects of elevated night pacing

##### Hypothesis

it will be explored whether there are sustained effects of elevated night pacing.

##### Analysis Methods

These analyses will be exploratory in nature, involving characterizing changes from baseline and end of therapy to the last follow-up visit. Generally speaking, all tests described above may be analyzed at week 12 compared to baseline, week 4 or week 8. Specific tests of interest will include

- For any measurement found significant at week 4
  - A test for subjects with high rate pacing set to OFF at week 4 will be done to compare the measurement at week 8 with both baseline and week 4

- A test for subjects for subjects with high rate pacing set to ON at week 4 will be done to compare the measurement at week 12 with baseline, week 4 and week 8
- For any measurement found significant by treatment at week 8
  - A test for subjects with rate pacing set to ON at week 4 will be done to compare the measurement at week 12 with baseline, week 4 and week 8

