As part of the exploratory/ancillary safety, tolerability and efficacy effects described in the REVAMP CIP, it will be of interest to characterize changes in collected measurements from Baseline to 4 weeks, compare changes in collected measurements at 4 weeks to 8 weeks in the subjects randomized to the elevated night pacing ON arm to subjects randomized to the elevated night pacing OFF arm and compare changes in collected measurements at 12 weeks to Baseline, 4 and 8 weeks to see whether any therapeutic improvements are sustained after the therapy is discontinued. If there are any nominally significant therapeutic effects at 4 or 8 weeks, those effects will specifically be explored further. Any effects that are significantly improved at 4 weeks compared to baseline will be explored at 8 and 12 weeks compared to baseline to determine if these effects are sustained. Similarly, any effects that are nominally significant between subjects on and off therapy between 4 and 8 weeks will be explored at 12 weeks to determine if improvements are sustained.

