## 7.5. Adjustments for Multiple Comparisons

No adjustments are planned for multiple comparisons.

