#### 7.9.9. Additional Exploratory Analyses

As this is a feasibility study with a relatively small sample size and no correction for multiple comparison, the ancillary objectives stated above were limited to the most likely possible outcomes predicted by the high rate pacing under investigation. There are many other potential exploratory analyses that could be of interest and could be performed. Foremost, although not explicitly stated in the protocol, it is possible that there might be no effect of the therapy at the 4 week follow-up visit, but that there is an effect of the therapy at the 8 week visit – particularly for those subjects with high rate pacing kept programmed to ON at the 4 week follow-up visit. Particularly for, but not limited to, any measurement that was trending towards significance at week 4, it will be of interest to test the 8 week measurement against the baseline measurement for significance of the change from baseline. If done, these tests should be performed analogously to the 4 week tests described within this section.

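### SAP 7.9.8 commits to persistence tests only for measures already nominally significant, and most of those tests reuse a visit from the test that selected them

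*SAP*

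**What the plan says.** SAP 7.9.8 (Sustained effects, Analysis Methods) sets two triggers for its specific tests.

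- **Week-4 trigger:** "For any measurement found significant at week 4". For subjects switched OFF at week 4, the test is to "compare the measurement at week 8 with both baseline and week 4". For subjects left ON, it is to "compare the measurement at week 12 with baseline, week 4 and week 8".
- **Week-8 trigger:** "For any measurement found significant by treatment at week 8". The ON subjects then get the same three week-12 comparisons.

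SAP 4.2 follows the same logic: "If there are any nominally significant therapeutic effects at 4 or 8 weeks, those effects will specifically be explored further". It goes on to say that effects significantly improved at 4 weeks will be examined later to learn whether they last. SAP 7.5 reads "No adjustments are planned for multiple comparisons".

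Other text loosens the trigger. SAP 7.9.8 calls the analyses exploratory and says "Generally speaking, all tests described above may be analyzed at week 12 compared to baseline, week 4 or week 8". SAP 4.2 and Protocol 6.2 also plan week-12 comparisons with baseline, week 4 and week 8 without any significance condition.

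**The concern.** Whether a benefit outlasts the therapy is a declared question of the study (Protocol 6.2 and 7.2). The week-4 test is a difference between week 4 and baseline. If it is significant only because baseline happened to be poor, week 8 or week 12 will also look better than that same baseline, and the effect appears sustained. If it is significant only because week 4 happened to be good, later visits will look worse than week 4, and the effect appears lost. Neither is new evidence, and the SAP does not warn the reader of this.

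The commitment is also uneven. For triggered measures the tests will be done; for the others they may be done. A measure that misses the trigger therefore has no assured persistence result, and what gets reported can depend on the earlier p-value.

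**Working it through.** **No figure to reproduce.** The SAP gives no error rate, power or visit correlation for these tests. An alpha of 0.05 appears only in model code.

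**Inputs from the documents**
- 30 subjects receiving elevated night pacing, randomised 2:1 (SAP 5.1), taken as 20 ON and 10 OFF.
- One-sided tests for MNLWHF and walk distance (SAP 7.9.4, 7.9.5); two-sided tests for safety measures, echo and biomarkers (SAP 7.9.2, 7.9.6, 7.9.7).

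**Assumptions**
- No effect at any visit, no attrition, normal data with equal variance.
- Nominal 5% for both the selecting test and the follow-up test.
- Visit correlation either equal between all visits or AR(1) from 0.5 to 0.9.

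**Why the tests are linked.** With equal visit correlation, two within-subject differences that share one visit correlate at 0.5. The week-4 test uses all 30 subjects and the follow-up uses one arm, so the correlation between the two mean changes is 0.5 × √(n_arm/30):
- ON, week 12 versus baseline: 0.5 × √(20/30) = 0.41
- OFF, week 8 versus baseline: 0.5 × √(10/30) = 0.29
- ON, week 12 versus week 8: no shared visit, so 0

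**Simulated rejection rates given a chance week-4 finding** (200,000 to 400,000 null trials per scenario; repeat runs agree to within about one percentage point). One-sided rates count the direction that would be read as sustained or lost. Two-sided rates count either direction.

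| Follow-up comparison | One-sided 5% | Two-sided 5%, equal correlation | Two-sided 5%, AR(1) 0.5 to 0.9 |
|---|---|---|---|
| ON week 12 vs baseline | about 18–21% across correlations | 13.2% | 12.3–14.5% |
| OFF week 8 vs baseline | about 13–17% across correlations | 8.4% | 10.2–12.0% |
| ON week 12 vs week 4 | about 18% equal correlation; about 6% at AR(1) 0.9 | 13.0% | 7.9% falling to 5.2% |
| OFF week 8 vs week 4 | about 14% equal correlation; 5–6% at AR(1) 0.9 | 8.4% | 6.1% falling to 5.0% |
| ON week 12 vs week 8 | 4.8% equal correlation; up to about 7% under AR(1) | 5.0% | 4.9–5.2% |

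Without selection, each comparison rejects at about 5%. After selection the mean ON week-12 change from baseline, truly zero, is biased by about 0.15 to 0.26 of a single-visit SD.

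**After a chance week-8 difference by arm (two-sided).** Under equal correlation, ON week 12 rejects in 9.3% against week 4, 9.3% against week 8 and 5.1% against baseline. Under AR(1) the three ranges are 11.8–13.6%, 5.2–6.3% and 7.3–10.3%.

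**Absolute size.** False week-4 finding followed by false ON confirmation against baseline, one-sided: 0.05 × 0.18 = 0.009, or 0.9% per null measure. Were the two tests independent it would be 0.05 × 0.05 = 0.0025, or 0.25%.

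**The case against.** The strongest reply is that this is a feasibility study. The SAP says it is not powered, discloses that nothing is adjusted and labels these analyses exploratory. Asking whether an effect lasts only after seeing one is a natural sequence, and the joint error is below 1% per measure. All of that stands and limits the weight of the point. It does not make a comparison that shares a visit with its trigger into separate evidence, and the SAP nowhere says so.

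A second reply is that dropping the trigger does not break the link. That is correct: among measures significant at week 4 by chance, the later interval against baseline excludes zero just as often as before. Read as tests, untriggered reporting would also give at least one rejection among the five comparisons in 20.7% of null measures, against 0.05 × 40.5% = 2.0% reached through the week-4 trigger (two-sided, equal correlation). This is why the fix asks for estimates rather than tests, and for an explicit caution.

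A reader might infer more than the documents support:
- **That the tests exceed a stated error rate.** The SAP states none; the 5% is an assumed benchmark.
- **That every follow-up test is inflated about threefold.** The size depends on arm, sidedness and visit correlation, and some comparisons show no inflation.
- **That untriggered measures are barred from testing.** SAP 7.9.8 permits all week-12 tests.
- **That SAP 7.9.9 confirms week-4 findings.** Its reference to "any measurement that was trending towards significance at week 4" is introduced as not limiting, the analysis is optional, and it looks for delayed effects where week 4 showed none.
- **That SAP 4.2 declares an effect sustained if a later test is significant.** It says only that such effects will be explored to determine this.

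**Conclusion.** The point holds as one of selective commitment and interpretation. Against baseline, a chance week-4 finding is followed by an apparent sustained effect in about 18 to 21% (ON, week 12) and 13 to 17% (OFF, week 8) one-sided, or about 12 to 15% and 8 to 12% two-sided in either direction. This part persists across the correlations tried.

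The apparent loss from week 4 is less secure. It is clearly inflated when visits are equally correlated and hardly at all under AR(1) 0.9, and the documents do not say which is closer. ON week 12 versus week 8 is essentially unaffected by the week-4 trigger. ON week 12 versus baseline is unaffected by the week-8 trigger only if visits are equally correlated.

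All rates are conditional on a false-positive week-4 or week-8 test and rest on the null, 20/10 and no-attrition assumptions. The point does not undermine the design, but the SAP should be amended on it.

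**What to change.** In SAP 7.9.8, replace both significance triggers with a list of measures fixed in advance, for example MNLWHF, walk distance, device-measured activity, end diastolic volume, mitral deceleration time, NT-proBNP, troponin and LVEF. For each, whatever the week-4 or week-8 p-value, report with confidence intervals:
- OFF arm: week-8 change from baseline and from week 4 (end of therapy).
- ON arm: week-12 change from baseline and from week 8 (end of therapy).

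Add a sentence to SAP 7.9.8, with a cross-reference from SAP 4.2, that a comparison sharing a visit with the week-4 or week-8 test is not independent confirmation that an effect was sustained or lost.

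The cost is SAP wording and some additional table rows, most of them likely null. No new data are needed. The list removes the selective reporting; only the added sentence deals with the shared visits, so both are needed.
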